5.4.1 Drug Extravasation

As a general recommendation, in the event of extravasation, the following advice should be considered:

- Stop the infusion immediately.
- Do not remove the needle or cannula.
- Aspirate with the same needle as much infiltrated drug as possible from the subcutaneous site.
- Apply ice to area for 15 to 20 minutes every four to six hours for the first 72 hours.
- Paint the skin over the extravasated site with 100% dimethyl sulfoxide (or hyaluronidase) four times daily for two weeks.

Watch the area closely during the following days in order to determine whether a surgical excision and skin graft is necessary.

5.5 General Concomitant Medication and Additional Assistance Guidelines

Concomitant treatment and prior medication are defined as non-investigational medicinal product (IMP). Concomitant treatment includes any prescribed medication or phytotherapy between the 28 days prior to the administration of the first treatment dose and the last safety visit during treatment period. All concomitant treatments will be recorded. After this time, information will only be collected on any anti-cancer drugs taken by the patient until EoS.

Information on concomitant medication will include start date, end date, brand or generic name, route of administration, dose, and treatment indication. The following concomitant treatments are permitted during the study:

- Erythropoiesis-stimulating agents (such as Procrit[®], Aranesp[®], Epogen[®]) for the supportive treatment of anemia. Blood transfusions are permitted during the study.
- The prophylactic use of granulocyte-Colony Stimulating Factor is not allowed during the first treatment cycle but can be used for cases of neutropenia arising during treatment, in accordance with the NCCN guidelines.
- Bisphosphonates and denosumab for the prevention of skeletal events.
- Prophylactic or therapeutic anticoagulation therapy such as low-molecular weight heparin or warfarin at a stable dose level.
- Mineralcorticoids (e.g., fludrocortisone).
- Medications for the treatment of diarrhea, nausea, anorexia, or vomiting.
- Any medications deemed necessary to ensure patient safety and well-being may be administered at the discretion of the Investigator.

5.6 Prohibited Concomitant Medications

INCMGA00012 (retifanlimab) belongs to the class of IgG antibodies that are administered parenterally and cleared by protein catabolism, extrinsic factors such as food and drug-drug interactions are not anticipated to affect its exposure. Specifically, drugs that affect cytochrome P450 and other metabolizing enzymes are not expected to interfere with the catabolism of INCMGA00012 (retifanlimab) (50). It is unlikely that INCMGA00012 (retifanlimab) would be a victim or a perpetrator of PK drug-drug interactions (51,52). Dedicated drug-drug interaction studies of retifanlimab have not been performed.

INCMGA00012 (retifanlimab) is known to increase some proinflammatory cytokine levels. This is a known class effect of checkpoint inhibitory monoclonal antibodies (mAbs) (53)(54) but is unlikely to modulate CYP enzymes or drug transporters, based on clinical evidence with other agents of this class (50). It is unlikely that retifanlimab would be a perpetrator of drug-drug interactions, and the potential for clinically significant drug-drug interaction is low.

HIV antiretroviral medications, used according to protocols as appropriate by HIV-positive participants in retifanlimab studies, may be substrates, inhibitors, or inducers of the P-glycoprotein and multidrug-resistant protein transporters and the cytochrome P450 enzyme system. None of the highly active antiretroviral therapies are immunosuppressors (55). Since retifanlimab is not expected to be a victim or perpetrator of drug transporters or cytochrome P450 enzymes, the potential of drug-drug interaction between antiretroviral drugs and retifanlimab is low (51). No clinically important differences in the CL of retifanlimab were found in HIV-positive participants taking antiretroviral medications compared to participants who were not HIV-positive.

Glucocorticoid co-administration was explored as a time series covariate in the population pharmacokinetics model. Results show that glucocorticoid co-administration is not a predictor for retifanlimab clearance in the model.

Hormonal contraceptives are metabolized by the cytochrome P450 enzyme system, and retifanlimab is not expected to be a victim or perpetrator of cytochrome P450 enzymes. Therefore, the potential for pharmacokinetic drug interactions between hormonal contraceptives and retifanlimab is low (56).

Subjects are prohibited from receiving the following therapies during the screening and treatment phase of this trial:

- Immunotherapy not specified in the protocol.
- Chemotherapy not specified in the protocol.

- Targeted therapy
- RT.

Note: RT is allowed during screening, as long as it is completed at least two weeks prior to first dose of study treatment and may be allowed to treat a symptomatic bone lesion or the brain after consultation with Sponsor.

- Herbal supplements.
- Probiotics.
- Live vaccines within 30 days prior to first dose of study treatment and while participating in the trial. Examples of live vaccines include, but are not limited to, the following: measles, mumps, rubella, varicella, herpes zoster, yellow fever, rabies, BCG, and typhoid (oral) vaccines. Seasonal influenza vaccines for injection are generally killed virus vaccines and are allowed. However, intranasal influenza vaccines (e.g., FluMist®) are live attenuated vaccines, and are not allowed.
- Immunosuppressive agents within seven days prior to first dose of study treatment.
- Steroids for any purpose other than to modulate symptoms from an event of clinical interest of suspected immunologic etiology.

Note: The use of physiologic doses of steroids (≤ 10 mg prednisone daily) is allowed and does not require Sponsor consultation.

Note: The use of systemic steroids to premedicate patients for whom computerized tomography (CT) scans with contrast are contraindicated is allowed. Magnetic resonance imaging (MRI) of abdomen and pelvis with a non-contrast CT scan of the chest may also be performed in these patients.

Note: Local applications and inhaled steroids for management of asthma are allowed.

Subjects who, per Investigator's assessment, require any of the aforementioned medications for clinical management should be discontinued from study treatment. There are no prohibited therapies during the post-treatment follow-up phase.

5.7 Medication Errors and Overdose

Medication errors in this study may arise when the drug is administered at the wrong time or when the wrong dose strength is taken. Patient medication errors should be recorded on the relevant section in the case report form (CRF). In the event of an error in the administration of the medication, the Sponsor should be informed immediately.

Medication errors must be reported irrespective of the presence of an associated AE/SAE, including:

- Medication errors involving patient exposure to the IMP.
- Any possible medication errors or use of the medication not defined in the protocol which implicates the participating patient or not.

Regardless of whether the medication error is accompanied by an AE or not, in the judgment of the Investigator, the medication error should be properly documented and recorded.

5.8 Treatment Compliance

Patients will receive treatment under physician supervision. Personnel will check the administration volume and total administered dose. The administered dose of each treatment will be recorded in the source data and the appropriate CRF.

6 STUDY ASSESSMENTS AND PROCEDURES

6.1 Informed Consent Form

Written ICF from the patient must be signed before performing any study procedure. However, tumor assessments available and performed as part of clinical practice prior to obtaining ICF and within 28 days prior to treatment start may be used; such evaluations do not need to be repeated for screening. Bone scans performed within 60 days prior to treatment start are acceptable.

By giving their consent, patients will be informed as to the nature of the study drug and will receive pertinent information regarding the study objectives, possible benefits, and potential AEs. They will also receive information on the follow-up procedures and possible risks they will be exposed to. This document also informs patients about how biological samples will be obtained and collected and its legal implications. After receiving the document, the patient will read it (or receive information verbally before witnesses) and will sign the previously approved ICF. The patient will receive a signed copy of the ICF. The patient can withdraw his consent and discontinue the study; this will not affect any future medical treatment. One re-screening is allowed in patients that are screening failure in this study. Patient has to re-consent ICF before any study procedure is done.

At inclusion:

- The Sponsor will request the patient's demographic and clinical data related to screening criteria.

- Each patient will be given a Unique Patient Number (UPN) for this study, provided by the Sponsor. All data will be recorded in the appropriate CRF using this identification number. This number will be provided to the central laboratory to ensure traceability of study samples.

Confirmation of patient's eligibility for study participation will be recorded on the CRF.

6.2 Visit Schedule

All screening tests and evaluations must be completed and reviewed to confirm that patients meet all eligibility criteria within 28 days prior to the first administration of study medication (dosing).

The Investigator will maintain a screening log to record details of all patients screened and to confirm eligibility or record reasons for screening failure, as applicable.

Visits are organized in programmed cycles of 28 days (if there are no delays in treatment owing to the occurrence of an AE). All visits must occur within ± 3 working days from the scheduled date, unless otherwise noted in the schedule of assessments.

Assessments scheduled for day 1 (before treatment) of all cycles must be performed within 72 hours prior to study treatment administration, unless otherwise indicated in the schedule of assessments, to confirm to the patient if treatment can be followed up. If a mandatory procedure described in the protocol falls on a bank holiday and/or weekend, this procedure should be performed on the day before or after the holiday (i.e. within a period of ± 3 working days). The summary of all study assessments is included in **Appendix 1**.

EoT visit will be performed within 28 days after last study treatment dose. Patients will be followed up for survival and post-study anticancer therapy evaluation every 3 months until the EoS. Telephone contact is acceptable.

6.3 Demographic Data and Medical History

Demographic data include age, and self-reported race/ethnicity. Medical history comprises clinically significant diseases, surgical interventions, history of cancer (including prior antineoplastic treatments and procedures), history of smoking, alcoholism, drug addiction, as well as any medications (e.g., prescribed drugs, over-the-counter drugs, medicinal plants, homeopathic remedies, or food supplements) used by the patient in the 28 days prior to screening visit.

6.4 Efficacy Assessments

6.4.1 Tumor and Response Evaluations

All measurable and evaluable lesions should be assessed and documented at the screening visit and re-assessed at each subsequent tumor evaluation. Tumor assessments will be performed at screening, every 8 weeks (± 7 days) for the first 6 months following first dose of study treatment, and every 12 weeks (± 7 days) thereafter until PD, treatment discontinuation, withdrawal of consent, the start of new anticancer treatment, death, or study termination by the Sponsor, whichever occurs first. The same radiographic procedures and technique must be used throughout the study for each patient.

Tumor assessment during the screening period should consist of clinical exam –with examination of the penis and/or inguinal region– and of anatomical imaging consisting of 1) CT scan of the chest, abdomen, and pelvis (MRI of the abdomen and pelvis with a non-contrast CT scan of the chest in patients for whom CT scans with contrast are contraindicated), 2) bone scan if a subject has a known history of bone metastases or has new bone pain during screening, and 3) any other imaging studies as clinically indicated by the treating physician [brain imaging during the trial should be performed in subjects with known brain metastases (every nine weeks for first year, then every 12 weeks) and those with worsening and/or new neurological symptoms].

Tumor assessment after the screening period should consist of clinical exam –with examination of the penis and/or inguinal region– and of anatomical imaging consisting of 1) CT scan of the chest, abdomen, and pelvis (MRI of the abdomen and pelvis with a non-contrast CT scan of the chest in patients for whom CT scans with contrast are contraindicated). In the event a positron emission tomography (PET)/CT scan is used for tumor assessments, CT portion of PET/CT is usually of lower quality, and should not be used instead of dedicated diagnostic CT. If the CT scan is of high quality, with oral and IV contrast, may be used with caution. Additional information from PET may bias CT assessment. 2) bone scan if a subject develops new or worsening symptoms or if the site believes they have attained a complete response (CR), and 3) any other imaging studies felt to be clinically indicated by the treating physician. All known sites of disease documented at screening should be re-assessed at each subsequent tumor evaluation.

After progression of disease by RECIST v.1.1, if the site Investigator determines the subject is clinically stable and will benefit from continued treatment, the subject will then be managed by irRECIST as described in **Section 6.4.4** of the protocol.

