--	---

	
HCV] are eligible only if polymerase chain reaction [PCR] is negative for virus hepatitis C ribonucleic acid [RNA]).
 
20. Known additional malignancy that is progressing or requires active treatment, or history of other malignancy within 3 years of study entry with the exception of cured basal cell or squamous cell carcinoma of the skin, superficial bladder cancer, prostate intraepithelial neoplasm, or other noninvasive or indolent malignancy, or cancers from which the participant has been disease-free for >1 year, after treatment with curative intent.
 
21. Patients have any other concurrent severe and/or uncontrolled medical condition that would, in the Investigator's judgment contraindicate patient participation in the clinical study.

Treatment:
	
After signing the ICF and confirmed eligibility, patients will receive INCMGA00012 (retifanlimab) 500 mg by intravenous infusion on Day1 of each cycle, once every four weeks for up to 2 years.
 
Patients will receive treatment until disease progression, unacceptable toxicity, death, or discontinuation from the study treatment for any other reason.
 
Patients discontinuing the study treatment period will enter a post-treatment follow-up period during which survival and new anti-cancer therapy information will be collected every 3 months (\pm 14 days) from the last dose of investigational product until the end of study (EoS).

Study Procedures, Efficacy and Safety Assessments:
	
Patient visits:
 
Visits are organized in programmed cycles of 28 days (if there are no delays in treatment owing to the occurrence of an AE). After baseline, all visits must occur within \pm 3 working days from the scheduled date, unless otherwise noted in the schedule of assessments, and every 12 weeks after documented PD.
 
Assessments scheduled for Day 1 of each cycle must be performed within 72 hours prior to study treatment administration, unless otherwise indicated in the schedule of assessments, in order to confirm to the patient if treatment can be followed up.
 
Efficacy assessments:
 
Tumor assessments will be performed until radiographically and/or clinically documented PD as per RECIST criteria v.1.1, study treatment discontinuation, initiation of new anticancer therapy, or discontinuation of patient from overall study participation (i.e., death, patient's request, lost to follow-up), whichever occurs first.

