	
Clinical assessment. Examination of the penis and/or inguinal region:
 
Radiographic assessment: [computerized tomography (CT) of the chest, abdomen, and pelvis or magnetic resonance imaging (MRI) of the abdomen and pelvis with a non-contrast CT scan of the chest in patients for whom CT scans with contrast are contraindicated] will be performed using RECIST v.1.1 every 8 weeks (\pm 7 days) from the first dose of study treatment up to 6 months (more frequently if clinically indicated). All subjects who remain on treatment for 6 months will subsequently have imaging performed every 12 weeks (\pm 7 days). Imaging should continue to be performed until radiologic evidence of PD, treatment discontinuation, the start of new anti-cancer treatment, withdrawal of consent, death, or the EoS, whichever occurs first. Bone scans will also be used to assess bone metastases. If a subject has a known history of bone metastases or has new bone pain during screening, a bone scan should be obtained prior to study entry. A bone scan at follow-up is required only if they develop new or worsening symptoms or if the site believes they have attained a complete response (CR). If a subject has no known metastatic disease in the bone or active symptoms, a bone scan at baseline is not needed.
 
After PD by RECIST v.1.1, if the site Investigator determines the subject is clinically stable and will benefit from continued treatment, the subject will then be managed by irRECIST.
 
Each assessment will be performed as scheduled according to the calendar regardless of any dosing delay to prevent the introduction of bias into the assessment of efficacy. Failure to perform any of the required disease assessments will result in the inability to determine disease status for that time point.
 
Tumor samples for molecular analysis are required for patient participation and patients must agree to provide tissues from a metastatic site or the primary penile tumor at the time of study entry (that should be available for at least 60% of patients) and at the time of PD. Provision of previous archival tissue is acceptable for patients with non-measurable disease, or inaccessible lesions.
 
Blood samples for molecular analysis will be collected at the time of baseline, after 2 cycles of study treatment (C3D1), and upon PD or EoS.
 
Safety assessments:
 
The occurrence and maximum grade of AEs observed throughout the study will be listed. Any AE that the Investigator reports as unrelated to the drug will also be reported. In this study, AEs will be assessed according to the NCI-CTCAE v.5.0.

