3 STUDY DESIGN

3.1 Description of Study Design

This is a multicenter, open-label, single-arm, phase II clinical trial to evaluate the efficacy and safety of the INCMGA00012 (retifanlimab) in progressive advanced PSqCC patients, previously treated or not with chemotherapy.

The study population consists of male patients age ≥ 18 years with advanced PSqCC that are presenting with progressive disease. Patients that have received prior treatment of locally recurrent and/or metastatic disease with platinum-based chemotherapy regimens are not excluded.

In the absence of progression of disease or unacceptable toxicity, treatment with INCMGA00012 (retifanlimab) will continue based on physician's criteria for up to 2 years.

Tumor assessments per RECIST v.1.1 and irRECIST will be performed approximately every eight weeks (± 7 days) for the first 6 months and every 12 weeks (± 7 days) thereafter until PD, treatment discontinuation, the start of new anti-cancer treatment, withdrawal of consent, death, or the end of study (EoS), whichever occurs first. Tumor assessments will be performed on the specified schedule regardless of treatment delays.

For estimation of ORR, CBR, DoR, and PFS tumor response will be based on RECIST v.1.1. In patients who continue treatment beyond radiographic PD per RECIST v.1.1, tumor response (ORR, CBR, and PFS) may continue to be assessed using irRECIST criteria until study treatment discontinuation.

Safety assessments will include the incidence, nature, and severity of AEs and laboratory abnormalities graded per the NCI-CTCAE v.5.0. Laboratory safety assessments will include the regular monitoring of hematology, blood chemistry, coagulation, and thyroid function testing. A schedule of assessments is provided in **Appendix 1**.

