3.2.4 Follow-up after treatment discontinuation

EoS will occur 12 months after the last patient has been enrolled in the study (treatment start).

Patients discontinuing the study treatment period will enter a post-treatment follow-up period during which survival and new anti-cancer therapy information will be collected every 3 months (\pm 14 days) from the last dose of investigational product until the end of study (EoS).

During this visit, status survival and post study anti-cancer therapy evaluation will be collected (telephone contact is acceptable).

LPLV: 12 months after first study dose of the last patient or progressive disease experienced in all patients or when the trial is terminated by the Sponsor, whichever is earlier.

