5.3 Treatment Modification

Safety and tolerability of all patients will be closely monitored throughout study treatment and the follow-up period using the NCI–CTCAE v.5.0. Patients will be assessed in order to detect any AEs before administering new study treatment during each treatment visit. Treatment will only be administered if clinical evaluation and local laboratory test results are acceptable.

Patients who have treatments withheld for more than 12 weeks must discontinue study treatment and are considered off study. Patients whose treatment is interrupted or permanently discontinued due to an AE, including abnormal laboratory value, must be followed until resolution or stabilization of the event, whichever comes first, which includes all study assessments appropriate to monitor the event.

Inpatient dose reductions are not permitted for INCMGA00012 (retifanlimab). If a dose interruption is necessary for management of treatment-related TEAEs, INCMGA00012 (retifanlimab) will be reinitiated at the dose at which it was interrupted.

Patients should meet the following re-treatment criteria before proceeding with subsequent cycles:

- Hemoglobin \geq 8 g/dL.
- ANC \geq $1.0 \times 10^9/L$.
- Platelet count \geq $75 \times 10^9/L$.
- ALT/AST/bilirubin level < Grade 2.
- Resolution of all immune-related TEAEs to \leq Grade 1 (with the exception of hyperglycemia [allowed to Grade 2] and endocrinopathy that is controlled on hormonal replacement).
- Resolution of all non-immune-related TEAEs to \leq Grade 1 or baseline (with the exception of Grade 2 alopecia and fatigue). Transient asymptomatic laboratory elevations \leq Grade 3 do not require dose interruption if the participant is asymptomatic and if the elevation is clinically insignificant and has been discussed with the medical monitor.

If retreatment criteria are not met, then re-treatment should be delayed, and the participant should be re-evaluated weekly or more frequently as clinically indicated. INCMGA00012 (retifanlimab) may be interrupted for a maximum of 12 weeks due to toxicity.

5.4 Modification of the Amount of Study Drug Administered Due to Changes in Patient's Weight

INCMGA00012 (retifanlimab) is administered as a fixed dose irrespective of the patient's body weight. AEs (both non-serious and serious) associated with INCMGA00012 (retifanlimab)

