- Absence of progressive tumor at critical anatomical sites (e.g., cord compression) requiring urgent alternative medical intervention.

In determining whether or not the tumor burden has increased or decreased per irRECIST, the local site Investigator should consider all target and non-target lesions as well as any incremental new lesion(s). Scenarios where PD is confirmed at repeat imaging if any of the following occur by irRECIST:

- Tumor burden remains $\geq 20\%$ and at least 5 mm absolute increase compared to nadir.
- Non-target disease resulting in initial PD is worse (qualitative assessment).
- New lesion resulting in initial PD is worse (qualitative assessment).
- Additional new lesion(s) since last evaluation.
- Additional new non-target progression since last evaluation.

If repeat imaging confirms PD due to any of the scenarios listed above, subjects will be discontinued from study therapy. If repeat imaging does not confirm PD by irRECIST and the

subject continues to be clinically stable, treatment may continue and follow the regular imaging schedule.

*Note: If a subject with confirmed radiographic PD per irRECIST, but the subject is achieving a clinically meaningful benefit, and there is no further increase in the tumor burden at the confirmatory tumor imaging, an exception to continue treatment may be considered following consultation with the Sponsor. In this case, if treatment is continued, tumor imaging should continue to be performed following the intervals as outlined in **Appendix 1**.*

*Note: In subjects who discontinue study treatment without documented PD, every effort should be made to continue monitoring their disease status by tumor imaging following the intervals as outlined in **Appendix 1** until the start of new anti-cancer treatment, PD, death, or the EoS, whichever occurs first.*

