Tumor assessments will be performed at baseline, every 8 weeks (\pm 7 days) for the first 6 months following first dose of study treatment, and every 12 weeks (\pm 7 days) thereafter, with additional scans as clinically indicated. All known sites of disease documented at screening should be re-assessed at each subsequent tumor evaluation. The same radiographic procedures and technique must be used throughout the study for each patient (bone scan will be performed only if a subject develops new or worsening symptoms or if the site believes they have attained a complete response).
7. In subjects who discontinue study treatment without documented disease progression, every effort should be made to continue monitoring their disease status by tumor imaging following the intervals as outlined in footnote 3 until the start of new anti–cancer treatment, disease progression, death, or the end of the study, whichever occurs first.

8. **Hematology/Chemistry:** Blood test will be performed as per local standard of care and clinical indication before treatment administration. These values should be included: hemoglobin, hematocrit, red blood cell count, platelet count, and WBC count with differential count (ANC, lymphocytes, monocytes, eosinophils, and basophiles), coagulation, chemistry with renal function analysis (serum creatinine or measured/calculated creatinine clearance or GFR), liver function (AST, ALT, ALP, GGT, total and direct bilirubin), glucose, sodium, potassium, calcium, chloride, magnesium, uric acid, total protein, albumin, and lactate dehydrogenase.
9. Cycle 1 Day 1 panel assessments are not required if the panel was performed at screening within 72 hours prior to start of study treatment.
10. **Viral serology:** HAV (IgM antibody), HBsAg, total HBcAb, HCV antibody; additional tests for HBV DNA or HCV RNA will be required to confirm eligibility; HIV.
11. **Mantoux or Quantiferon tuberculin skin test (TST):** in case of positivity of the test results, the pulmonologists must rule out the presence of latent TBC. All patients with latent TBC will be excluded from the study.
12. **Urinalysis:** Urinalysis include specific gravity, pH, glucose, protein, ketones, and blood. Every 2 cycles: Cycle 1 day 1, Cycle 3 day 1, cycle 5 day 1, cycle 7 day 1, etc., before study treatment administration.

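### The documents disagree on whether imaging, and with it PFS and DoR follow-up, continues after treatment stops without progression

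*Protocol*

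**What the plan says.** **Imaging ends with treatment.**
- The synopsis lists, among the events that end tumour assessment, "study treatment discontinuation, initiation of new anticancer therapy, or discontinuation of patient from overall study participation". Its radiographic paragraph says "Imaging should continue to be performed until radiologic evidence of PD, treatment discontinuation", followed by further stopping events.
- Protocol 3.1 has "until PD, treatment discontinuation, the start of new anti-cancer treatment, withdrawal of consent, death, or the end of study (EoS), whichever occurs first", and SAP 1.4 repeats that rule.
- Protocol 6.4.1 has "until PD, treatment discontinuation, withdrawal of consent, the start of new anticancer treatment, death, or study termination by the Sponsor, whichever occurs first".
- The PFS definition in Protocol 6.4.3 has event-free patients assessed only up to treatment discontinuation and censored at their last evaluable scan.

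**Imaging continues.**
- The closing note of Protocol 6.4.4 says that for patients who stop without documented progression "every effort should be made to continue monitoring their disease status by tumor imaging", until new therapy, progression, death or end of study.
- Footnote 7 in Protocol Appendix 1 and footnote 7 in SAP 1.5 ask the same, "following the intervals as outlined in footnote 3". Footnote 3 is weight, height and vital signs in the protocol, and concomitant medication in the SAP. The imaging intervals are in footnote 6 of both.

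**Study status.** Protocol 5.3 says patients whose treatment is withheld for more than 12 weeks "must discontinue study treatment and are considered off study". Protocol 3.2.4 says "Patients discontinuing the study treatment period will enter a post-treatment follow-up period", with survival and new-therapy information every 3 months until end of study. Imaging is not in that list.

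**Censoring.** Protocol 8.6 censors PFS and DoR at the last tumour assessment, with no time window. SAP 5.4.1.1 and SAP Table 2 censor event-free patients at the last evaluable imaging up to 35 days after the last dose: PFS in both places, DoR in Table 2. The TTP definition in SAP 5.4.1.1 has the same window, although SAP 5.7 drops TTP as an endpoint. The PFS censoring table in SAP 5.4.1.1 also has a row that censors discontinuation for toxicity or another reason at the last radiological assessment.

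**The concern.** Two sites can each follow the protocol and collect different data on the same kind of patient. One stops scanning when treatment stops; the other scans to progression. The patients concerned stop without progression, many presumably for toxicity and some while responding, so the point at which their follow-up ends may be related to their later course. SAP 5.4.5 rests the Kaplan-Meier analyses on dropout being unrelated to prognosis.

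The endpoints at stake are the secondary ones: PFS, 6-month PFS and DoR. Scans that were never taken cannot be recovered at analysis. Scans that were taken may still be set aside by the SAP's censoring rules.

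**Working it through.** **Step 1. The plan's own figures.** With 16 evaluable patients and success at 3 or more responders, the exact one-sided alpha at an ORR of 5% is 0.0429 and the power at 25% is 0.803. Then 16/0.9 = 17.8, rounded up to 18. The sample size reproduces and this point does not touch it.

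**Step 2. One patient through the rules.** Take a patient who stops for toxicity without progression.

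| Sections followed | Scans after stopping | PFS and DoR |
|---|---|---|
| Protocol 6.4.1, 3.1, synopsis, 6.4.3 | None | Censored at the last on-treatment scan, unless he dies |
| Protocol 6.4.4 note with Protocol 8.6 | Yes | Event at progression or death; otherwise censored at the last scan, whenever taken |
| Protocol 6.4.4 note with the SAP | Yes | No event: censored within the 35-day window, so later clean scans are dropped. Later progression: an event under the SAP definitions, which set no time limit, but for PFS censored under the toxicity row |

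The SAP does not say which of its statements prevails in the last case.

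**Step 3. Deaths.** Protocol 8.6 and SAP Table 2 censor an event that follows two or more missed scheduled assessments. If scans after discontinuation count as scheduled and are not done, a later death can be censored at the last earlier scan. If none are scheduled, the same death is an event. The conflict can thus change the result from identical data.

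**Step 4. How many patients.** The documents give no expected number for this trial. Protocol 1.6.3 reports discontinuation for treatment-emergent adverse events in:
- Study 101: 26/289 = 9.0%
- the anal-canal carcinoma study: 7/94 = 7.4%
- Study 203: 13/121 = 10.7%
- Study 104: 0 of 6

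Part of section 1.6.3 was not available in the text reviewed, so the list may be incomplete. Assume the range of the three larger studies applies here:
- Expected number: 18 × 0.0745 = 1.3 to 18 × 0.1074 = 1.9.
- Chance of at least one: 1 − (1 − 0.0745)^18 = 75% to 1 − (1 − 0.1074)^18 = 87%.

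**Step 5. 6-month PFS.** Protocol 8.4.7 reports this as a simple proportion, so each patient's status at 6 months must be known. One patient is 1/18 = 5.6 percentage points, but only if he stops before 6 months without progression or death. The documents do not allow that timing to be estimated.

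**Step 6. DoR.** At the 25% target, 18 × 0.25 = 4.5 responders are expected; take 3 to 5 and assume the same discontinuation rates in responders.
- Chance that at least one stops for an adverse event: 1 − (1 − 0.0745)^3 = 21% to 1 − (1 − 0.1074)^5 = 43%.
- Expected number at 4.5 responders: 4.5 × 0.074 = 0.33 to 4.5 × 0.107 = 0.48.
- If it happens, one patient is 1/5 = 20% to 1/3 = 33% of the DoR set.

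**The case against.** **Required versus best-effort scans.** The note in 6.4.4 and footnote 7 are best-effort texts, so required imaging might end at discontinuation with optional imaging after it. The wording of 3.1 and 6.4.1, where the first listed event ends imaging, does not support this, nor does the PFS definition in 6.4.3. Even if accepted, it leaves the data dependent on site practice.

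**Uniform censoring by the SAP.** The 35-day window and the toxicity row apply to every site, so the analysis might treat all such patients alike. This stands in part. It shows that editing the imaging text alone would not bring later scans into the analysis. But the SAP is unclear about progression seen after a toxicity stop, it carries both imaging rules itself (1.4 and footnote 7 of 1.5), and it differs from Protocol 8.6.

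**Limited stakes.** This stands. There is one arm, so no treatment comparison can be biased; what can be biased is the level of the PFS and DoR estimates. Secondary p-values are declared descriptive.

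**Survival follow-up.** A reader might infer from the off-study wording in 5.3 that OS data will be lost. The documents do not support that. The synopsis, 3.2.4 and 6.2 provide survival follow-up every 3 months until end of study, by telephone if need be (3.2.4 and 6.2), and 5.3 itself goes on to require follow-up of patients stopped for an adverse event. OS would be lost only if a site took those words literally.

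**Conclusion.** The contradiction is real and should be resolved. For patients who stop treatment without progression, the documents give two imaging rules and two sets of censoring rules, and the result for PFS, 6-month PFS and DoR depends on which are used. Early censoring of these patients may be informative; the documents cannot show that it would be.

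The size is modest: about 1 to 2 of 18 patients, with a 21% to 43% chance that a responder is among them. This rests on three assumptions: that the adverse-event discontinuation rates of the three larger quoted studies carry over, that there are 3 to 5 responders, and that responders stop at the same rate as others. Stops for other reasons are not counted.

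Two stronger readings should not be drawn. One is that the primary result is at risk: SAP 5.4.1.1 counts best response only up to 35 days after the last dose, so ORR is little affected. The other is that every toxicity stop costs 5.6 points of 6-month PFS, which holds only under the condition in Step 5.

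**What to change.** 1. Adopt one rule for the end of imaging and use it everywhere. The rule consistent with the follow-up already requested in the 6.4.4 note and Appendix 1 footnote 7 is obtained by deleting treatment discontinuation from the stop lists in both synopsis paragraphs, Protocol 3.1, Protocol 6.4.1 and SAP 1.4, and aligning the PFS definition in Protocol 6.4.3.
2. In the SAP, remove the 35-day cut-off and the toxicity-censoring row for PFS and DoR, or keep them only as a sensitivity analysis, so that later scans count as they do under Protocol 8.6. State that progression on a scan after discontinuation is an event.
3. Correct footnote 7 in Protocol Appendix 1 and in SAP 1.5 to point to footnote 6.
4. Reconcile the off-study wording in Protocol 5.3 with the survival follow-up in 3.2.4, and say which follow-up continues for these patients.

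The cost is a wording amendment, minor SAP reprogramming and a few more scans at sites that now stop. Because 3.2.4 lists only survival and new-therapy information and allows telephone contact, imaging should be named there as well.
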